9.1 Dose Limiting Toxicity

For the patients enrolled in the phase Ib trial, the occurrence of dose limiting toxicity (DLT) and the type of DLT will be tabulated by dose level, and overall.

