### Trial design:

Multicenter, open label Phase Ib/IIa study consisting of 2 parts:

- A part 1 dose escalation phase lb to confirm the safety of IPH2201 as a single agent during 4 weeks and thereafter combined with ibrutinib during 52 weeks
- · A part 2 single-arm phase IIa assessment of IPH2201 combined with ibrutinib during 52 weeks

During the phase lb, a 3+3 design will be employed. Four doses are planned to be assessed if MTD is not previously reached:

Dose level 1: 1 mg/kg Dose level 2: 2 mg/kg Dose level 3: 4 mg/kg

Dose level 4: 10 mg/kg

[figure not shown]
Three patients will be entered at each dose level. If a Dose Limiting Toxicity (DLT) is encountered in the initial cohort at a given dose level, that cohort will be expanded to a total of 6 patients.

Release date: Edition number 12 August 2016 MOD-3783

**GED** version

MTD will be considered to have been exceeded if >1/6 patients experience a DLT at that same dose level. MTD will be sought at the previous dose level by enrolling 3 additional patients, unless this cohort has been previously expanded to 6. If less than 2 out of 6 patients develop a DLT at that level, it will be defined as the MTD.

Dose-escalation will be based on a review by the safety committee of the data from all patients of the *current* cohort, after they have completed first 2 cycles of single agent IPH2201.

Introduction of ibrutinib at a new dose level will be allowed by the safety committee after review of the data of all patients of the *previous* cohort, after they have completed 2 cycles of IPH2201 in combination with ibrutinib.

During the phase IIa, patients will receive IPH2201 in combination with ibrutinib from the first day of the phase IIa.

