# 4.3.2 Patient Replacement Policy

In any case, if patients do not receive at least 1 administration of IPH2201.

In the two phases of the trial (Ib and IIa), in case of treatment discontinuation of IPH2201 due to disease progression before the end of 8 weeks of treatment.

Release date: Edition number

GED version

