- To recommend the discontinuation of the study, transiently or permanently, or a decrease in the dose, after the occurrence of 2 unacceptable reactions in patients treated by the combination of IPH2201 and ibrutinib during the first or second phase of the study

DLTs and unacceptable reactions are defined as:

- Any grade 3 or grade 4 non hematologic toxicity
- o Grade 4 neutropenia (ANC < 500/μI) lasting ≥7 days after discontinuation of therapy in patients with pre-treatment ANC ≥ 1,000/μI
- o Grade 4 thrombocytopenia (platelet count <20,000/μl and/or ≥75% decrease from pre-treatment value)
- Grade 3 or 4 thrombocytopenia associated with bleeding
- Any dose delay due to AE for > 14 consecutive days

Such events will be considered as DLTs whenever they occurred during the first 4 cycles (8 weeks) of treatment in phase Ib (including 2 administrations of treatment with IPH2201 alone and 2 administrations of treatment with IPH2201 + ibrutinib).

Release date: Edition number

GED version

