4.1 General comments

Data will be analyzed using SAS (Version 9.3 or higher). Graphs will be produced in SAS or R.

No tests of significance will be carried out to compare treatment arms on baseline data. Descriptive statistics will be tabulated as follows:

- Categorical data will be summarized in contingency tables presenting frequencies and percentages. By default, those percentages will be calculated on the number of patients in the analysis population.
- Continuous data will be summarized using number of non-missing values (n), mean, standard deviation, median, first and third quartiles, minimum and maximum values.

For phase Ib results, all tables will be presented by dose level and overall. For Phase II, there will be only 1 column. Listings with individual values will be provided for all data presented in the tables.

The patients treated during the phase Ib with the phase IIa recommended dose will be analyzed in all the outputs of both phases of the trial.

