4.2 Definition of Populations

4.2.1 Intent-to-treat (ITT) / safety population

The safety population will be equivalent to the ITT population and will include all patients who have received at least one dose of monalizumab. All patients will be analyzed according to the first dose of monalizumab they received.

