4.6 Methods To Be Used For Handling Missing Data

Missing data will not be imputed

5. Study Patients

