The Kaplan-Meier method will be used to display graphically the DOR, PFS and OS for all patients. The number of patients and the number of DOR, PFS and OS events will also be displayed on the graph. The median (with its 95% confidence interval) DOR and DCOR will be displayed. Listing with individual values will also be displayed.

Page 19 of 26

TPL N°: eTPL SA-02-01

TPL Version: 02

Of SOP SA-02.08 TPL Effective Date: 31 Mar 2016

[figure not shown]

9. Safety Evaluation

All safety analyses will be done for the ITT/safety population.

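### The SAP tabulates DLTs on all treated patients with no DLT-evaluable set, so dosed patients with an incomplete 8-week window lower the reported DLT proportion

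*SAP*

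**What the plan says.** DLT occurrence and identification of the MTD, alone and in combination with ibrutinib, form one of the two phase Ib primary endpoints (Protocol 3.1.1; SAP 3.1.1.1). The DLT analysis is one sentence in SAP 9.1: "the occurrence of dose limiting toxicity (DLT) and the type of DLT will be tabulated by dose level, and overall".

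That section names no denominator, but the general rules supply one:

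- SAP 9: "All safety analyses will be done for the ITT/safety population".
- SAP 4.2.1: that population "will include all patients who have received at least one dose of monalizumab".
- SAP 4.1: "By default, those percentages will be calculated on the number of patients in the analysis population".
- SAP 4.6: "Missing data will not be imputed".

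The endpoint has a fixed observation window. Protocol 9.3: "Such events will be considered as DLTs whenever they occurred during the first 4 cycles (8 weeks) of treatment in phase Ib". The same sentence specifies two administrations of IPH2201 alone and two with ibrutinib, which starts at week 4 (Protocol 3.3.2).

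Protocol 4.3.2 replaces patients in two situations only: no IPH2201 received, or "in case of treatment discontinuation of IPH2201 due to disease progression before the end of 8 weeks of treatment".

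**The concern.** The analysis set asks for one dose. The endpoint needs 8 weeks of observation and four administrations. Someone who withdraws consent at week 3 has had no combination treatment, yet counts in full in the denominator of a table meant to describe toxicity alone and in combination.

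At 3 to 6 patients per level, one such patient visibly moves the percentage. Where no DLT occurs the percentage is 0% either way, but a reader of the table cannot tell whether 0/3 means three completed windows or two.

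The SAP already fits a population to its endpoint elsewhere. The main endpoint population (SAP 4.2.2) requires 52 weeks between first dose and data cutoff, and it drops early progressors. The phase Ib DLT endpoint has no counterpart.

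**Working it through.** **Plan's own figure.** The protocol synopsis gives 12 to 24 phase Ib patients. Four dose levels × 3 = 12 and 4 × 6 = 24, so it reproduces. Neither document states a DLT rate, an early-exit rate or a 3+3 operating characteristic, so there is no planned DLT figure to check.

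**Who is counted.** Applying SAP 4.1, 4.2.1, 4.6 and 9 with Protocol 4.3, 4.3.2 and 9.3 to a phase Ib patient who leaves before week 8:

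| Situation | Replaced? | In denominator? | In numerator? |
|---|---|---|---|
| Never dosed | Yes | No | No |
| Dosed, IPH2201 stopped for progression, no DLT | Yes | Yes | No |
| Dosed, consent withdrawal, investigator decision or major deviation, no DLT | Not provided for | Yes | No |
| Dosed, left after a DLT | No, unless IPH2201 was stopped for progression | Yes | Yes |

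Rows two and three are the problem. No sentence calls these patients DLT-free. That follows from the default denominator together with the absence of imputation.

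**Size.** Let x be the patients with a DLT, n the treated patients at a level, and e those with an incomplete window and no DLT.

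- Tabulated proportion: x/n
- Proportion among evaluable patients: x/(n − e)
- Ratio of the first to the second: (n − e)/n

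The values of x and e below are assumed for illustration.

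| Case | Tabulated | Evaluable | Ratio |
|---|---|---|---|
| x = 1, n = 6, e = 1 | 1/6 = 16.7% | 1/5 = 20.0% | 5/6 |
| x = 1, n = 6, e = 2 | 1/6 = 16.7% | 1/4 = 25.0% | 4/6 |
| x = 2, n = 6, e = 1 | 2/6 = 33.3% | 2/5 = 40.0% | 5/6 |
| x = 2, n = 7, e = 1 (replaced progressor) | 2/7 = 28.6% | 2/6 = 33.3% | 6/7 |

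With e = 0 the two columns agree. With x = 0 both are 0% and only the number of observed windows differs.

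**The case against.** The strongest objection concerns consequence. A reader might infer that the SAP 9.1 table supplies the DLT rate behind the MTD, so that the denominator could let a toxic dose through. The documents do not support that. The MTD comes from a 3+3 count and safety committee review during the trial (Protocol synopsis, Trial design, and 9.3), whereas SAP 9.1 is a descriptive table. The threshold is also a count: "MTD will be considered to have been exceeded if >1/6 patients experience a DLT at that same dose level". Taking a leaver out of the table turns 17% into 20%, but one DLT remains one DLT. This objection stands, and the point is limited accordingly.

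Second, many early exits are already covered. Early progressors are replaced. Grade 3 or 4 non-hematologic toxicity is itself a DLT, as is a delay due to an AE of more than 14 consecutive days. Except after consent withdrawal, patients are followed for a period after treatment stops (Protocol 4.3). This narrows the gap without closing it:

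- Replacement does not remove a dosed progressor from the safety set.
- Follow-up off treatment does not provide the missing combination administrations.
- Protocol 3.3.1 takes a phase Ib patient off study when a grade 3 or higher AE has not resolved to grade 2 or lower after a 2-week suspension, while the delay criterion needs more than 14 days. On that wording, an exit at day 14 for grade 3 neutropenia need be neither a DLT nor a replacement.

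Third, SAP 4.1 promises individual listings and SAP 5.1 gives discontinuation reasons by dose level, so a careful reader could rebuild the evaluable denominator. That is true, but a primary endpoint should not depend on the reader doing so.

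**Conclusion.** The point holds for the reported DLT proportion. The stated analysis set does not fit the endpoint's 8-week, four-administration window, and every incomplete patient without a DLT lowers the tabulated figure. In the illustrated cases the reduction is about 3 to 8 percentage points (16.7% against 20.0% or 25.0%; 33.3% against 40.0%; 28.6% against 33.3%).

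These sizes assume one or two incomplete patients at a level, and that such a patient adds nothing to the evaluable figure. If every patient completed the window, there is no effect.

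The point does not extend to the MTD decision. To calculate how often the 3+3 rule would pass a toxic dose, one would have to assume a true DLT rate, an exit rate, and that the committee counts an unobserved patient as observed. The documents state none of these. The protocol does leave a related gap: it has the committee review all patients of a cohort after they have completed their cycles, but does not say whether an unreplaced early leaver counts among the 3 or 6. Those passages need to be reconciled, and the SAP table does not settle the question either way.

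**What to change.** - **SAP 4.2:** add a DLT-evaluable set, made up of phase Ib patients who had a DLT or who completed the 8-week window with the planned administrations.
- **SAP 9.1:** tabulate DLTs by dose level and overall on that set, with the all-treated table as support. Report the number not evaluable at each level, with reasons.
- **Protocol:** reconcile the 3+3 counting text and the replacement policy with the completed-cycles review, so that the status of an unreplaced early leaver is explicit. How such a patient should be handled is for the sponsor and safety committee to settle.

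The SAP change costs one definition and one more table, with slightly smaller denominators and no new data collection. The evaluable proportion leans upward, because partly observed windows without a DLT are dropped while any DLT is kept. Showing both tables lets the reader see the range.

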9.2 Extent of Exposure

The following outcomes will be summarized descriptively:

- Number of doses received per patient, both as categorical and continuous variable, for monalizumab and ibrutinib
- Duration of treatment for monalizumab and ibrutinib.
 - For monalizumab: if a patient discontinued prematurely from treatment, the duration of treatment is defined as the time between the date of first administration of study drug and the day before the next planned dose administration of study drug (in Months). The way of calculating the next planned dose administration is the same as for patients who did not discontinue from treatment. If a patient did not discontinue prematurely from treatment, the duration of treatment is defined as the time between the date of first administration of study drug and the date of last administration of study drug + 27 days (in Months) if the next administration is planned after Week 8; for the patients who remained under protocol version 4.0 until end of study and for patients under protocol version 5.0 with a next planned administration on or before Week 8, the duration of treatment is defined as the time between the date of first administration of study drug and the date of last administration of study drug + 13 days (in Months)
 - For ibrutinib: the duration of treatment is defined as the time between the date of first administration of study drug and the date of last administration of study drug (in Months).
- Number of patients experiencing a monalizumab dose reduction at the lower dose level
- Number of patients experiencing at least one dose administration delayed for monalizumab
- Number of patients experiencing at least one interruption during drug administration for monalizumab

Page 20 of 26

TPL N°: eTPL SA-02-01 Of SOP SA-02.08 TPL Effective Date: 31 Mar 2016

- Number of patients experiencing at least one interruption of ibrutinib
- Number of patients who had an ibrutinib dose reduction from 3 capsules (420 mg) to 2 capsules (280 mg) and number of patients who had an ibrutinib dose reduction to 1 capsule (140 mg)

9.3 Adverse Events

Adverse events (AEs) will be coded using the Medical Dictionary for Regulatory Activities and will be graded according to the National Center Institute Common Terminology Criteria for AEs (NCI-CTCAE criteria [v4.0] [3]). Adverse events will be analyzed in terms of their type, incidence, severity and relationship to the study treatment. Related AEs are defined as events with a relationship to study treatment equal to 'possibly related', 'probably related', or 'definitively related' or with missing relationship.

Adverse events in this section will be tabulated if they are treatment-emergent (TE), see definition in Section 4.4. Partial dates will be handled according Section 4.5.

A summary table will present the frequency of patients with at least one:

- TEAE
- TEAE related to monalizumab or ibrutinib
- TEAE related to monalizumab
- TEAE related to ibrutinib
- TEAE causing monalizumab or ibrutinib discontinuation
- TEAE causing monalizumab discontinuation
- TEAE causing ibrutinib discontinuation
- TEAE causing dose delayed of monalizumab
- TEAE causing monalizumab infusion interrupted
- TEAE causing dose reduction of monalizumab at the lower dose level
- TEAE causing dose reduction of ibrutinib
- TEAE causing dose interruption of ibrutinib
- Grade 3 or worse TEAE
- Serious TEAE
- Monalizumab or ibrutinib related serious TEAE
- Monalizumab related serious TEAE
- Ibrutinib related serious TEAE
- Fatal TEAE
- Fatal TEAE related to monalizumab or ibrutinib

In addition, tabulations of the number of patients who experienced TEAEs as well as severity of the events will be presented by SOC and PT, by grade, by dose and overall. Patients will only be counted once for each preferred term. In case a patient experienced the same event more than once, the worst severity will be presented.

The following tabulations will be presented:

TPL Version: 02

[figure not shown]
- All TEAEs
- Monalizumab or ibrutinib related TEAEs
- Monalizumab related TEAEs
- Ibrutinib related TEAEs
- TEAE causing monalizumab or ibrutinib discontinuation
- TEAE causing monalizumab discontinuation
- TEAE causing ibrutinib discontinuation
- TEAE causing dose reduction of monalizumab at the lower dose level
- TEAE causing dose reduction of ibrutinib
- Grade 3 or worse TEAE
- Serious TEAEs
- Monalizumab or ibrutinib related Serious TEAEs
- Monalizumab related Serious TEAEs
- Ibrutinib related Serious TEAEs
- Fatal TEAE

Listings of serious adverse events will be provided, flagging the ones that are TE, including the patient identifier, verbatim, preferred term, duration of the event, severity, action taken, outcome, causality, and date of onset.

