### Part 1: phase lb

### Primary endpoint:

The primary endpoint will be the safety of 2 repeated administrations of IPH2201 given as a single agent during 4 weeks, and thereafter, given in combination with ibrutinib during 52 weeks:

- Occurrence of DLT and identification, if any, of the MTD, during the administration of IPH2201 as a single agent and given in combination with ibrutinib
- o Occurrence of AEs and SAEs

Safety will be assessed using the CTCAE version 4.03, apart from neutropenia and thrombocytopenia for which severity will be graded by using the IWCLL grading scale reported in appendix IV. It will include a descriptive analysis of the frequency and severity of AEs; related AEs followed to resolution (grade  $\leq$  1) unless deemed irreversible and clinical laboratory tests collected to assess lab abnormalities, as well as results of vital sign measurements, electrocardiograms (ECGs), physical examinations and imaging studies.

Release date: Edition number 12 August 2016 MOD-3783

[figure not shown]
GED version

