# 3 STUDY DESIGN

### 3.1 STUDY ENDPOINTS

# 3.1.1 Primary Endpoints

Part 1: phase lb

The primary endpoint will be the safety of 2 repeated administrations of IPH2201 given as a single agent during 4 weeks and, thereafter, given in combination with ibrutinib during 52 weeks:

- Occurrence of DLT and identification, if any, of the MTD, during the administration of IPH2201 as a single agent and given in combination with ibrutinib
- Occurrence of AEs and SAEs

Safety will be assessed using the CTCAE version 4.03, apart from neutropenia and thrombocytopenia which severity will be graded by using the IWCLL grading scale reported in appendix IV. It will include a descriptive analysis of the frequency and severity of AEs, as well as clinical laboratory tests collected to assess lab abnormalities, results of vital sign measurements, electrocardiograms (ECGs), physical examinations and imaging studies. Related AEs will be followed to resolution (≤ grade 1) unless deemed irreversible.

Part 2: phase IIa

The primary endpoint will be the rate of complete response, achieved with a combination of IPH2201 and ibrutinib, assessed 52 weeks after the beginning of the treatment, defined according to the guidelines of IWCLL (Hallek, Cheson et al. 2008), and confirmed by a bone marrow biopsy.

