# 7.2.2 Progressive disease

Progressive disease during or after treatment is characterized by at least one of the following:

- o Lymphadenopathy. Progression of lymphadenopathy is often discovered by physical examination and should be recorded. In CLL, the use of CT scans usually does not add much information for the detection of progression or relapse. Therefore, the use of imaging methods to follow CLL progression is at the discretion of the investigator. Disease progression occurs if one of the following events is observed:
  - Appearance of any new lesion, such as enlarged lymph nodes (>1.5 cm), splenomegaly, or other organ infiltrates
  - An increase by 50% or more in greatest determined diameter of any previous site.
- An increase in the previously noted enlargement of the liver or spleen by 50% or more or the de novo appearance of hepatomegaly or splenomegaly
- An increase in the number of blood lymphocytes by 50% or more with at least 5000 B lymphocytes per microliter
- Transformation to a more aggressive histology (e.g., Richter syndrome). Whenever possible, this diagnosis should be established by lymph node biopsy
- Occurrence of cytopenia (neutropenia, anemia, or thrombocytopenia) attributable to CLL
  - During treatment. Cytopenias may occur as a side effect of many therapies and should be assessed according to the Grading scale for hematologic toxicity in CLL studies (see appendix IV). During treatment, cytopenias cannot be used to define disease progression
  - After treatment. The progression of any cytopenia (unrelated to autoimmune cytopenia), as documented by a decrease of hemoglobin levels by more than 20 g/L (2 g/dL) or to less than 100 g/L (10 g/dL), or by a decrease of platelet counts by more than 50% or to less than 100 x10^9/L (100,000/µL), which occurs at least 3 months after treatment, defines disease progression, if the marrow biopsy demonstrates an infiltrate of clonal CLL cells

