# 9.1 ADVERSE EVENT

#### 9.1.1 Definitions

The definitions of Adverse Events (AEs) and Serious Adverse Events (SAEs) are given below. It is the responsibility of the PI to ensure that all staff involved in the study are familiar with the content of this section.

The occurrences of AEs and SAEs are recorded from the time of signed informed consent until the end of the study. All AEs will be graded according to the Common Terminology Criteria for Adverse Events (CTCAE) of the NCI, version 4.03 (June 14, 2010).

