# APPENDIX IV: GRADING SCALE FOR HEMATOLOGIC TOXICITY IN CLL STUDIES

According to the IWCLL guidelines (Hallek M, Blood 2008).

Decrease in platelets 1 or		
	Hb ‡ (nadir) from	Absolute neutrophil
Grade*	pretreatment value, %	count/µL§ (nadir)
0	No change to 10%	≥ 2000
1	11%-24%	≥ 1500 and < 2000
2	25%-49%	≥ 1000 and < 1500
3	50%-74%	≥ 500 and < 1000
4	≥ 75%	< 500

\*Grades: 1, mild; 2, moderate; 3, severe; 4, life-threatening; 5, fatal. Death occurring as a result of toxicity at any level of decrease from pretreatment will be recorded as grade 5.

†Platelet counts must be below normal levels for grades 1 to 4. If, at any level of decrease, the platelet count is  $< 20 \times 109/L$  (20 000/  $\mu$ L), this will be considered grade 4 toxicity, unless a severe or life-threatening decrease in the initial platelet count (e.g., 20 < 109/L [20 000/  $\mu$ L]) was present pretreatment, in which case the patient is not evaluable for toxicity referable to platelet counts.

‡Hb levels must be below normal levels for grades 1 to 4. Baseline and subsequent Hb determinations must be performed before any given transfusions. The use of erythropoietin is irrelevant for the grading of toxicity but should be documented.

f the absolute neutrophil count (ANC) reaches < 1 x 109/L (1000/  $\mu L$ ), it should be judged to be grade 3 toxicity. Other decreases in the white blood cell count, or in circulating neutrophils, are not to be considered because a decrease in the white blood cell count is a desired therapeutic endpoint. A gradual decrease in granulocytes is not a reliable index in CLL for stepwise grading of toxicity. If the ANC was < 1 x 109/L (1000/  $\mu L$ ) before therapy, the patient is not evaluable for toxicity referable to the ANC. The use of growth factors such as G-CSF is not relevant to the grading of toxicity, but should be documented.

Release date: Edition number

GED version

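### SAP 9.3 grades every adverse event by CTCAE, while the protocol's phase Ib primary safety endpoint grades neutropenia and thrombocytopenia by the IWCLL scale; a grade shift can be shown for thrombocytopenia

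*SAP*

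**What the plan says.** **SAP.** Section 9.3 states that adverse events "will be graded according to the National Center Institute Common Terminology Criteria for AEs". It names no exception. The tables by term and grade, and those of events of grade 3 or worse, rest on that grading. The supplied SAP text does not mention the IWCLL hematologic toxicity scale. The SAP introduction says that the plan is based on protocol version 5.0.

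**Protocol, with the exception.** The synopsis defines phase Ib safety by CTCAE 4.03, "apart from neutropenia and thrombocytopenia for which severity will be graded by using the IWCLL grading scale reported in appendix IV". Section 3.1.1 repeats it: "apart from neutropenia and thrombocytopenia which severity will be graded by using the IWCLL grading scale reported in appendix IV". The synopsis entry for the phase IIa secondary safety endpoint carries the same exception. Section 7.2.2 also sends cytopenias during treatment to Appendix IV.

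**Protocol, without the exception.** Section 9.1.1 says: "All AEs will be graded according to the Common Terminology Criteria for Adverse Events (CTCAE) of the NCI". Section 3.1.2 (phase IIa safety), section 9.2.2 (which restates the phase Ib primary endpoint) and section 11.3.3 (grading by the investigator) likewise give CTCAE alone. Sections 9.1.2 and 9.1.4 refer to CTCAE terms.

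**Appendix IV.** Platelet grades are set by percent fall from the pretreatment value, with the condition that "Platelet counts must be below normal levels for grades 1 to 4"; a count under 20,000/µL is generally grade 4. Neutrophil grades use absolute counts. A patient whose ANC was below 1,000/µL before therapy is set aside: "the patient is not evaluable for toxicity referable to the ANC". A similar rule covers a severely low initial platelet count, "in which case the patient is not evaluable for toxicity referable to platelet counts".

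**The concern.** Occurrence of adverse events, described by frequency and severity, is part of the phase Ib primary endpoint. Where the endpoint text names one scale for two cytopenias and the SAP applies another, the severity tables for those terms do not report the endpoint as defined, and the SAP gives no reason for the change.

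The choice of scale matters in this disease. Exclusion criterion 4 bars low counts only when they are not due to CLL marrow failure, so patients with low baseline platelets or neutrophils can enter. For them a scale relative to baseline and a scale of absolute counts can give different answers. The cohorts are also small. At a dose level of 3 or 6 patients, moving one patient across the grade 3 line changes that row by 1/3 = 33% or 1/6 = 17%; in the 27-patient phase IIa set it is 1/27 = 3.7%. The safety committee takes safety data into account when it selects the phase IIa dose.

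**Working it through.** The plan has no figure of its own to reproduce here. The check compares the texts and then works through Appendix IV.

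**1. Platelet grade by Appendix IV.** Percent fall = (baseline − nadir) / baseline × 100. The bands are 11–24% grade 1, 25–49% grade 2, 50–74% grade 3, and 75% or more grade 4. Take one nadir of 50,000/µL, assumed below the laboratory's normal range:

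| Baseline (/µL) | Fall | Appendix IV grade |
|---|---|---|
| 200,000 | 150,000/200,000 = 75% | 4 |
| 100,000 | 50,000/100,000 = 50% | 3 |
| 60,000 | 10,000/60,000 = 17% | 1 |

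If a scale uses the absolute count only, all three patients have the same count and so the same grade, whatever the cut-offs.

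**2. Where the two kinds of scale agree.** Suppose the absolute scale starts grade 3 at a count T. Appendix IV starts grade 3 at half the baseline, so the two coincide only when baseline = 2T. The documents do not give T. Over an assumed range:

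| Assumed T (/µL) | Baseline at which the scales agree (/µL) |
|---|---|
| 25,000 | 50,000 |
| 50,000 | 100,000 |
| 75,000 | 150,000 |

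Away from that baseline the shift can go either way. With T = 50,000 for illustration:
- From 200,000 to 80,000 is a fall of 120,000/200,000 = 60%. That is grade 3 by Appendix IV (if 80,000 is below normal) but does not reach T.
- From 60,000 to 40,000 is a fall of 20,000/60,000 = 33%. That is grade 2 by Appendix IV but is past T.

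**3. Neutropenia.** Appendix IV uses absolute counts: grade 3 from 500 to below 1,000/µL and grade 4 below 500/µL. Without the CTCAE cut-offs, no difference in grade can be derived. What can be shown is evaluability. Appendix IV removes patients with a baseline ANC below 1,000/µL, whereas SAP 4.1 by default divides by everyone in the analysis population. As an illustration, with one event in a cohort of 6 of whom one other patient is not evaluable, the rate is 1/6 = 17% by the SAP and 1/5 = 20% by Appendix IV.

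**4. Dose-limiting toxicities.** The grade 4 neutropenia and grade 4 thrombocytopenia items in protocol 9.3 carry their own count limits, and the platelet limits match Appendix IV grade 4. The item for grade 3 or 4 thrombocytopenia with bleeding gives no grade 3 limit and names no scale. SAP 9.1 tabulates occurrence and type of DLT, not grade.

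**The case against.** The strongest reply is that the SAP follows the protocol's own recording rules. Sections 9.1.1 and 11.3.3 have adverse events graded by CTCAE, and sections 9.2.2 and 3.1.2 describe safety by CTCAE alone. That stands, in that the fault is not the SAP's alone. It does not remove the gap: section 3.1.1 and the synopsis define the endpoint, their exception is specific, and the SAP neither applies it nor explains dropping it.

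A second reply is that the analyses are descriptive, the phase IIa decision rests on the number of complete responses, and no stated decision rule uses the TEAE grade tables. This limits the consequence, but for phase Ib the description of severity is itself part of the primary endpoint.

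A third reply is that a laboratory abnormality becomes an adverse event only under the conditions in protocol 9.1.2 and 9.1.4, so grades derived from counts do not map one-to-one onto reported events. That stands, and the fix has to allow for it.

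Several stronger readings are tempting but unsupported:
- *No cytopenia table will follow the endpoint.* The supplied SAP text passes from 9.4 to 9.6, so laboratory tables may exist that are not visible here. The point covers only the adverse event tables in 9.3.
- *Neutropenia grades shift as well.* The documents show only the evaluability and denominator difference.
- *Many patients are affected.* Low counts are permitted at entry, but no figure says how common they are.
- *DLT counts or the MTD are wrong because of SAP 9.3.* The grade 4 items have their own limits. Only the bleeding item depends on an unnamed scale, and that gap lies in the protocol.

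**Conclusion.** The point holds for the SAP 9.3 by-grade and grade 3 or worse tables, for neutropenia and thrombocytopenia. For thrombocytopenia the possible size is large for an individual patient: the same nadir of 50,000/µL spans grades 1 to 4 under Appendix IV according to baseline. The contrast with CTCAE rests on the assumption that CTCAE grades platelets by absolute count alone. For neutropenia the demonstrated effect is confined to who is evaluable and who is in the denominator. How many patients would be regraded cannot be estimated from the documents.

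The protocol's internal contradiction is a separate matter that needs its own correction. Grade also triggers suspension of IPH2201 (section 3.3.1) and interruption of ibrutinib (section 3.3.2), so this review does not say which scale should govern treatment decisions.

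**What to change.** **In SAP 9.3:**
- Regrade reported neutropenia and thrombocytopenia TEAEs by Appendix IV from the hematology counts, with the SAP 4.4 baseline as the pretreatment value. Use these grades in the by-grade and grade 3 or worse tables. Keep CTCAE for every other term.
- State how a count is linked to an event, for example the lowest count between the event's start and end dates, and what is done when no count falls in that window.
- Add one Appendix IV laboratory-grade summary, so that low counts not reported as adverse events are also shown. Remove patients who are not evaluable under Appendix IV from its denominators, separately for neutrophils and platelets, and give their number.

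The cost is SAP wording, a short derivation and one more table. No new data are needed, because hematology is scheduled at every visit in both flow charts.

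**In the protocol:** reconcile the synopsis, 3.1.1 and 7.2.2 with 3.1.2, 9.1.1, 9.2.2 and 11.3.3, and check the CTCAE references in 9.1.2 and 9.1.4. State which scale the thrombocytopenia-with-bleeding DLT item uses. This means a protocol amendment, and the sponsor and investigators should settle it with the treatment rules in view. If the sponsor intends CTCAE for the safety endpoint after all, the synopsis and 3.1.1 must say so; either way the protocol and SAP must agree.
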